9.2 Quality Control

QC processes are the activities that occur on a day to day basis to ensure that the data entered into the database is accurate and complete.

The QC team has developed a QC plan based on our own experiences during the conduct of previous clinical trials.

The site has developed specific templates for all visits which are guided by the case report forms and we have also implemented 3 different levels of the QC process.

Level 1 QC- Source documents and CRF completion

Rapid QC of source documentation is done Real-time. At this point the source documentation is checked for completeness at the end of the day but before the patient leaves the clinic. If any information obtained during patient interview is missing and needs to be addressed immediately, it is flagged by the QC assistant and the relevant staff obtains the information. Other missing information that does not need immediate attention is flagged and reviewed at a later time-point. After receipt of laboratory results (2-3 days), the CRF's are completed and QC is conducted for CRF completeness. At level 1, all queries are resolved within (2-3 days) of the patient visit.

Level 2 QC – Detailed review of Source documentation and CRF's

At this level all information transcribed onto the CRF's are checked for accuracy and verified in the source documents. All Transcription errors are corrected at this time-point. If any information cannot be verified, the relevant staff members are asked to add a note to file to clearly explain the error or incorrect information.

Level 3 QC- Computer system generated

This level of QC occurs during data capturing. The data management system prompts for any missing information that is required. If this information is not completed on the CRF, the data team refers these queries back to the QC team who resolves them accordingly.

10. STATISTICAL CONSIDERATIONS

10.1 Method of Randomisation

Enrolled participants will be assigned at random, to one of the two study treatment arms in equal proportions. The randomisation list used to assign individual study participants to one of the two treatment arms will be generated by the protocol statistician, using randomly permuted blocks. The randomisation statistician will provide the study pharmacy with sealed, opaque randomisation envelopes, sequentially labelled by PID. These envelopes will be assigned in sequential order to eligible study participants. Upon opening the envelope the pharmacist will add her name and signature as well as the time and date the envelope was opened. This being an open label study, the treatment assignment of a participant will be known by the participant and the study staff.

10.2 Outcome Measures

Main Outcome Measure:

 Renal Function estimated by Serum Creatinine Clearance, adverse pregnancy outcomes (e.g., stillbirth, preterm delivery at < 37 weeks gestation, low birth weight <2,500 grams, and congenital anomalies) and Bone Mineral Density among women

Bone Mineral Density and growth parameters in neonates and infants until cessation of breastfeeding.

Other Outcome Measures:

- Confirmed presence of HIV infection detected by HIV NAT positivity at scheduled 3 monthly visits until 18 months.
- Adherence -self reported use of study product and pill count
- Partners HIV status at enrollment confirmed by Two POC tests and Adherence measured at delivery and 18 months postdelivery
- Antiretroviral drug level in plasma as a marker of adherence.
- Presence of viral resistance mutations that have been selected by Truvada (K65R, M184V) in participants who acquire HIV infection
- Mother to child transmission-reactive NAT testing performed in children born to mothers who acquire HIV infection during pregnancy and post-delivery.

Behavioural Risk:

- Number of sexual partners with whom participant had unprotected intercourse during pregnancy and postnatally
- Number of protected and unprotected acts of intercourse during pregnancy and postnatally
- Sexually transmitted infections acquired during pregnancy
- Sexually transmitted infections acquired postnatally
- Facilitators and barriers to adherence.

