Approximately 12 months for planned accrual and 24 months for complete follow-up. The study period is expected to span 3 years.

Study Products:

Truvada (emtricitabine 200mg/tenofovir disoproxil fumarate 300mg) is in a fixed-dose combination (FDC) tablet formulation and is proven safe for the prevention and treatment of HIV in non-pregnant and non-lactating women.

Study Arms:

Arm A: (Intervention)

Standard HIV Prevention strategy **PLUS** a once daily dose of Truvada (FTC 200mg/TDF 300mg tablet) initiated in pregnancy and continuing until cessation of breastfeeding or 18 months postdelivery whichever is earliest and thereafter the option to continue PrEP post breastfeeding cessation.

Arm B: (Control)

Standard HIV Prevention strategy throughout pregnancy until 18 months postdelivery **PLUS** the offer to initiate PrEP post breastfeeding cessation.

Primary Objective:

• To compare the frequency and seriousness of specific adverse events related to TDF/FTC in women and their children in Arm A (exposure to TDF/FTC) and Arm B (no exposure to TDF/FTC) during pregnancy until breastfeeding cessation.

Secondary Objectives:

- To estimate HIV incidence in women in ARM A with ARM B at delivery and at 18 months post-delivery.
- To determine the interdependency of adherence to a once daily oral TDF/FTC regimen and standard HIV prevention methods during pregnancy and postdelivery.
- To measure antiretroviral drug (TDF/FTC) level in women and their infants in association with adherence, safety and level of protection (plasma and breastmilk)
- To detect drug resistance among women who acquire HIV infection and correlate the treatment outcomes (after initiating immediate ARV treatment) with drug resistance
- To determine mother-to-child transmission of HIV among women who acquire incident infections during pregnancy and breastfeeding and the frequency of drug resistance in their infected babies

Main Outcome Measure:

 Serum Creatinine Clearance, adverse pregnancy outcomes (e.g., stillbirth, preterm delivery at < 37 weeks gestation, low birth weight <2500 grams, and congenital anomalies) and Bone Mineral Density among women Bone Mineral Density and growth parameters in neonates and infants until 18 months of age.

Other Outcome Measures:

- Confirmed presence of HIV infection detected by HIV NAT at scheduled 3 monthly visits until 18 months.
- Adherence –self reported use of study product, pill count during pregnancy and postdelivery

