To explore the safety of Truvada when used as PrEP in combination with current recommendations for prevention of sexually transmitted infections and HIV in young women at substantial risk of HIV acquisition during pregnancy and lactation.

2.2 Primary Objective:

 To compare the frequency and seriousness of specific adverse events related to TDF/FTC in women and their children in Arm A (exposure to TDF/FTC) and Arm B (no exposure to TDF/FTC) during pregnancy until breastfeeding cessation.

2.3 Secondary Objectives:

- To estimate HIV incidence in women in ARM A with ARM B at delivery and at 18 months post-delivery.
- To determine the interdependency of adherence to a once daily oral TDF/FTC regimen and standard HIV prevention methods during pregnancy and postdelivery.
- To measure antiretroviral drug (TDF/FTC) level in women and their infants in association with adherence, safety and level of protection (plasma and breastmilk)
- To detect drug resistance among women who acquire HIV infection and correlate the treatment outcomes (after initiating immediate ARV treatment) with drug resistance
- To determine mother-to-child transmission of HIV among women who acquire incident infections during pregnancy and breastfeeding and the frequency of drug resistance in their infected babies

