6.12 HIV Prevention Post Breastfeeding Cessation

Participants in both arms will be offered PrEP post breastfeeding cessation until end of study at 18 months after the last participant enrolled has delivered. Thereafter, participants who remain at high risk will be referred to the nearest Dreams PrEP Demonstration site or the National PrEP Program site whichever is available at the time of study completion. The study is expected to be complete by June 2019. We believe that there would be at a minimum ONE PHC or NGO that will be a PrEP service delivery site in Umlazi by the time of study completion. PrEP is slated to be included in the PEPFAR-supported DREAMS initiative focused on young women and adolescent girls. PrEP is also included in the National Strategic Plan (NSP) for HIV, STIs and TB (2012-2016).

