7.21 Procedures for Assessing Safety

Participants will be asked one month after starting Truvada and at each subsequent scheduled visit whether they have had any admissions to hospital, or suffered from any significant illness that required medical attention. The site clinician will determine whether an illness meets the criteria for Serious Adverse Event (SAE) Reporting. SAEs will be reported to the UKZN BREC, Medicines Control Council and Department of Health. Participants will also be asked whether they have experienced any side effects.

Clinical assessments during pregnancy will be conducted as per the national guidelines for maternity care.

Maternal safety assessments during pregnancy and until 74 weeks study exit: All women will have bloods drawn for chemistry and haematological investigations at screening, enrolment, 2 weeks, 4 weekly until delivery, <72 hours of delivery, 2 weeks post delivery, 6 weeks, 10 weeks, 14 weeks and 4 weekly until 74 weeks (inclusive). Chemistry tests include liver function markers (ALT/AST/Phosporous), renal function (serum creatinine/urea/sodium/potassium), and bone density markers (serum calcium and magnesium).

Bone mineral content in the mother will be measured by DXA scan at 6 weeks postpartum, 6 months, 12 months and 18 months. Both Hip and Spine DXA scans will be done at above scheduled visits.

Within 72 hours of delivery, the participant with her maternity care record (MCR) will be reviewed by the study clinician. Fetal outcome in addition to other obstetric data will be extracted from the MCR. The following definitions will be used to document fetal outcome:

NON-VIABLE FETUS (MISCARRIAGE)

Less than 28 weeks* gestation and where there is no evidence of life at delivery. **STILL BIRTH** Gestational age of 28 weeks or more and where there is no evidence of life at delivery. **NEONATAL DEATH**** Death after a live birth whatever the duration of the pregnancy. **When the gestational age is not known, a legal weight cut-off of 1000 g is used.**

Maternal gestational age will be determined by clinical and obstetric assessments that will include an Ultrasound, measurement of symphysis fundal height and last menstrual date if known. Preterm delivery is defined as < 37 weeks. Moderate preterm delivery 32-35 weeks and severe preterm delivery <32 weeks.

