The primary objective is to compare the frequency and seriousness of adverse events in women receiving tenofovir/emtricitabine in pregnancy and their newborn as opposed to women not receiving tenofovir/emtricitabine during pregnancy and their newborn. The number of adverse events experienced during pregnancy and post-delivery will be summarized for each of the study arms. This will also be stratified by seriousness of the adverse event. The number of adverse events will be compared between the study arms using Fisher's Exact test. Furthermore we will use the most widely used approach to test equivalence, namely the two one-sided test (TOST) procedure (Schuirmann DJ. A comparison of the two one-sided tests procedure and the power approach for assessing equivalence of average bioavailability. J Pharmacokin Biopharm. 1987;15:657–680. doi: 10.1007/BF01068419). Furthermore we will also employ a hierarchical or random effects modeling approach for a non-inferiority analysis for the primary endpoints.

A secondary objective is to compare the number of incident HIV infections in women during pregnancy alone and thereafter during breastfeeding. The analysis will be stratified by levels of PrEP adherence, partner involvement, condom usage and relationship dynamics. The cumulative incidence and associated 95% confidence intervals will be calculated for each study arm. The number of incident events will be compared for statistical difference between the study arms using Fisher's Exact test.

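### Infant bone and growth outcomes have two end times, one of which cuts follow-up at weaning; separately, the maternal safety analysis has no end, although either arm may take or stop PrEP after weaning

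*Combined protocol and SAP*

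**What the plan says.** **Infants.** The main outcome measure in the synopsis is "Bone Mineral Density and growth parameters in neonates and infants until 18 months of age". Section 10.2 lists the same outcome as "Bone Mineral Density and growth parameters in neonates and infants until cessation of breastfeeding". Both are current text. Section 7.21 and Appendix 6 schedule infant DXA at 6 weeks and at about 6, 12 and 18 months, whatever the feeding status. Section 7.13 dates cessation of breastfeeding 28 days after the last exposure to breast milk.

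**Mothers.** The primary objective (2.2) compares women and children "during pregnancy until breastfeeding cessation". Neither the synopsis nor 10.2 clearly attaches an end time to maternal creatinine clearance or bone density. Section 7.21 sets "Maternal safety assessments during pregnancy and until 74 weeks study exit", with maternal DXA at 6 weeks and 6, 12 and 18 months. In 10.4, "The number of adverse events experienced during pregnancy and post-delivery will be summarized for each of the study arms"; no end is given.

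**After weaning.** Section 6.12 states: "Participants in both arms will be offered PrEP post breastfeeding cessation until end of study". Under 7.11, Arm A women may stop and Arm B women may start.

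**Analysis.** Section 10.4 analyses all randomised participants by intention to treat, using Fisher's exact test, two one-sided tests and a non-inferiority model. It notes that the smaller differences seen under intention to treat can work the wrong way in such designs. It adds a per-protocol analysis but does not define the population or its censoring.

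**The concern.** There are two separate problems.

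First, one main infant outcome has two windows. Under 10.2, an infant's later scans count or not according to when the mother weans, which is a post-randomisation event in an open-label trial. Weaning could differ by arm: Arm B women are offered PrEP only once they stop breastfeeding, whereas Arm A women have it either way. If it does differ, the infants left in the 10.2 window at 12 and 18 months are no longer the randomised groups.

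Second, the exposure contrast between mothers holds by design only until weaning. If 10.4 is read as running to study exit, late visits may compare Arm A women who have stopped with Arm B women who have started. Section 1.10 reports that bone density moved back towards baseline off drug, so the direction for bone is plausible. In a trial that aims to show no excess harm, a contrast pulled towards zero favours the claim of safety.

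**Working it through.** **1. The plan's own figure.** Inputs from 10.3: true and reference rate 18.5%, margin 7.5 points, two-sided 5%, 80% power, unpooled Z test.

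n = (1.96 + 0.8416)² × 2 × 0.185 × 0.815 / 0.075² = 7.849 × 0.30155 / 0.005625 = 420.8, so 421 per arm. This matches. Preterm delivery is settled at birth, so no choice of postnatal window changes it.

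**2. Infant scans inside each window** (four scheduled: 6 weeks, 6, 12 and 18 months).

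| Cessation of breastfeeding | Kept under 10.2 | Kept under synopsis |
|---|---|---|
| before 6 weeks | 0 | 4 |
| 6 weeks to 6 months | 1 | 4 |
| 6 to 12 months | 2 | 4 |
| 12 to 18 months | 3 | 4 |
| 18 months or later | 4 | 4 |

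The lost scans are ones the plan already schedules.

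**3. Maternal outcomes.** Let uA and uB be PrEP uptake after weaning in each arm. The documents give neither, so all values are assumptions.

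*Outcomes read at a visit (bone density; the same logic applies to creatinine).* Suppose the on-drug loss has reached a plateau, a share r of it is recovered by Arm A women who stop, and a share l is incurred by Arm B women who start. The share of the contrast kept at 18 months is f = 1 − (1 − uA)r − uB·l. Section 10.3 cites a lumbar spine contrast of −3.16%, from HIV-infected women, used here for scale only.
- uA = 1, uB = 0.25, r = l = 0.25: f = 0.94, contrast −2.96%.
- uA = uB, r = l = 0.25: f = 0.75, contrast −2.37%.
- uA = uB, r = l = 0.5: f = 0.50, contrast −1.58%.

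*Consequence for a non-inferiority claim.* Take a generic comparison with 80% power at zero difference and a true on-drug difference equal to the margin. The chance of a false claim is Φ(2.8016(1 − f) − 1.96): 2.5% at f = 1, 4.6% at 0.9, 10.4% at 0.75 and 28.8% at 0.5. Section 10.3 works out no power against a margin for maternal bone density, so these figures are illustrative.

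*Event rates per person-time.* Take 6 antenatal plus 18 postnatal months (the periods in the HIV calculation in 10.3) and weaning at b months. The share of the rate difference kept is [6 + b + (uA − uB)(18 − b)] / 24. With equal uptake this is 12/24 = 50% at b = 6, 18/24 = 75% at b = 12, and 24/24 = 100% at b = 18.

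*Cumulative risk.* Suppose the 3% v 1% chemistry figures in 10.3 are the risks up to weaning at 6 months, with the same rates over the remaining 12 months.
- Equal 50% uptake: Arm A 1 − 0.97 × 0.98 = 4.94%; Arm B 1 − 0.99 × 0.98 = 2.98%. The difference is 1.96 points, almost unchanged. The risk ratio falls from 3.0 to 1.66. Power to detect a difference at 421 per arm falls from 54% to 31% (normal approximation).
- Uptake 25% in A and 50% in B: difference 1.5 points.
- Uptake 50% in A and 25% in B: difference 2.45 points, larger than before weaning.

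Attenuation is therefore expected for visit-based measures and, with equal uptake, for rates. It is not expected in general for a cumulative risk difference.

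**The case against.** **The infant window in 10.2 matches exposure.** Infants receive no drug through milk after weaning, so scans at 18 months include unexposed time and an early effect may have faded. This is true. It supports reporting each scheduled age, so that the early scans are seen separately; it does not support dropping scans by weaning date. For the same reason, a reader might infer that post-weaning PrEP contaminates the infant contrast. It does not.

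**The maternal window is already set.** The primary objective ends at breastfeeding cessation, and 10.4 introduces the adverse-event analysis by restating that objective. Reading 10.4 as running to 18 months is therefore an inference. A reader might also conclude that all the main safety outcomes have two stated end times. Only infant bone density and growth do; the maternal end is unstated in the outcome lists and open in 10.4.

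**The plan anticipates the problem.** Section 10.4 recognises the risk with intention to treat, adds a per-protocol analysis, and promises a full analysis plan before analyses begin. That weakens any suggestion that the window will be chosen after the data are seen. But 10.4 says it describes the primary safety endpoint here, so the window belongs here. An Arm B woman who accepts PrEP after weaning is following protocol, so an undefined per-protocol set need not remove her.

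**Ending the maternal comparison at weaning has the same weakness as 10.2 does for infants.** This stands. Maternal DXA starts at 6 weeks, so a woman who weans earlier has no scan in the window. That is why a fixed-visit comparison is needed beside it.

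**A larger effect might be inferred from the chemistry figures.** A reader might spread 3% and 1% over all follow-up, put weaning halfway, and conclude that late data halve the excess. On that model the risks up to weaning are 1.5% v 0.5%, already a 1-point difference, and with equal uptake it is 1 point over the longer window too. Stopping at weaning gives a standard error of √[(0.015 × 0.985 + 0.005 × 0.995)/421] = 0.00685. The chance of meeting a 2-point margin is then Φ(0.01/0.00685 − 1.96) = 30.9%. The longer window has a larger standard error and so a lower chance. The excess is smaller because exposure is shorter, not because late data were added.

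**Conclusion.** The infant point is a plain contradiction within a main outcome. The 10.2 version discards up to four of the four scheduled scans according to a post-randomisation event. Fixed-age follow-up to 18 months, as in the synopsis, is the less biased choice, and the data are already planned.

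The maternal point is real but smaller. The objective and the analysis section do not agree on an end, and exposure after weaning is a matter of choice in both arms. Late intention-to-treat comparisons of bone density and creatinine may be attenuated in the direction that favours a claim of safety. Keeping 50% to 94% of the contrast is what the assumed inputs above give; it is not an estimate. The documents give no post-weaning uptake and no expected weaning age for the safety outcomes. They say only that breastfeeding for at least a year is encouraged (1.11), and the HIV calculation in 10.3 assumes 18 months. At 18 months there is no dilution.

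A reader might infer that the trial as a whole is biased towards finding safety. The documents do not support that: preterm delivery, the other birth outcomes and the 421 per arm are untouched.

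**What to change.** **Infants (10.2).** Replace the cessation window with analysis of bone density and growth at the scheduled fixed-age visits (6 weeks, 6, 12 and 18 months) for all infants as randomised, matching the synopsis. Name one date for the last visit: 7.13 gives 74 weeks, while Appendix 6 gives 72.

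**Mothers (synopsis, 10.2, 10.4).** State the end time for creatinine clearance, bone density and adverse events.
- Align the 10.4 comparison with the primary objective, ending at breastfeeding cessation.
- Report post-weaning maternal data separately as supportive, and draw no non-inferiority or equivalence claim from them alone.
- Add a fixed-visit comparison as randomised, because weaning may differ by arm.
- Report weaning time by arm.
- Define the per-protocol set and its censoring, including how PrEP taken after weaning is handled.

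**Cost.** Wording in the synopsis, 10.2 and 10.4, with no new visits, scans or participants. The price is fewer late scans in the maternal comparison that ends at weaning, which is partly offset by the fixed-visit comparison.

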10.3 Sample Size Calculation

In view of the limited evidence of safety data from studies of PrEP (TDF/FTC) use in pregnancy, we based our sample size on data provided in studies of ART treatment in HIV infected pregnant women. In few studies, comparisons were made to HIV uninfected pregnant women.

To compare the frequency and seriousness of adverse events in women receiving tenofovir/emtricitabine in pregnancy as opposed to women not receiving tenofovir/emtricitabine in pregnancy, we have based our sample size on the main clinically relevant pregnancy outcome.

Adverse Pregnancy Outcomes

Although all pregnancy outcomes will be compared between the intervention (immediate PrEP) and control (deferred PrEP) groups, we based our sample size on the expected preterm delivery proportion among HIV uninfected women (South Africa 18.5%, Botswana 19%). A sample size of 421 in the Immediate PrEP group and 421 in the Deferred PrEP group (i.e. 842 in total) achieves 80% power to detect a non-inferiority margin difference between the group proportions of 0.075 or 7.5%. The reference group proportion (deferred PrEP) of pre-term delivery pregnancy outcome as a main clinically-relevant adverse event is 0.185 or 18.5%.

Maternal Adverse Events (2% margin difference)

Other maternal adverse events will include abnormal chemistry (Grade \geq 2) results. As reported in the PROMISE study, Grade 2 or higher chemistry abnormalities were significantly higher in HIV infected pregnant women randomized to TDF containing ART (3%) compared to AZT/sdNVP (1%) (p<0.03).

Maternal and Infant Bone Mineral Density (4-7% margin difference)

We have also used the PROMISE study findings to determine the required sample size for reporting other clinically relevant adverse events such as maternal and infant bone mineral content. In the P1084s study, a substudy of PROMISE mothers, the lumbar spine BMD declined significantly more through week 74 in the maternal TDF-ART arm compared to the infant NVP arm; mean (95% CI) percent change -2.06% (-2.90, -1.23) versus +1.09% (0.11, 2.07), mean difference -3.16% (-4.44, -1.87) (p-value< 0.001). Similarly, hip BMD declined significantly more through week 74 in the maternal TDF-ART arm compared to the infant NVP arm; mean (95% CI) percent change -5.37% (-5.99, -4.76) versus -3.05% (-3.72, -2.38), mean difference of -2.33% (-3.23, -1.42) (p-value< 0.001). We would require 150 infants exposed to maternal PrEP (TDF/FTC) and 150 infants unexposed (control group) based on 80% power to detect a pair-wise difference of 4-5% in mean WB-BMC and 6-7% in mean LS-BMC.

PASS 12 sample size software (Hintze, J. (2013). PASS 12. NCSS, LLC. Kaysville, Utah, USA. www.ncss.com) was used to calculate the samples sizes for testing equivalence between the treatment and control groups (Blackwelder WC. "Proving the null hypothesis" in clinical trials. Controlled clinical trials. 1982 Dec 31;3(4):345-53). We assumed equal adverse events rates (proportions) across the two groups i.e. zero difference and a maximum D (difference) of 7.5% for equivalence of the two groups. The table below displays the sample sizes required to achieve a 80% power with $\alpha = 0.05$ to establish equivalency for various adverse birth outcome prevalences based on actual data from the same setting published recently (Moodley, Theron et al. "Improved Pregnancy Outcomes with Increasing Antiretroviral Coverage in South Africa." BMC Pregnancy and Childbirth 16 (2016): 35. PMC. Web. 3 Mar. 2016). Based on the largest observed adverse birth outcome prevalence for pre-term delivery yields the largest required sample size i.e. 421 per group or 842 in total based on the assumptions mentioned above.

Based on current data (maternal adverse events, maternal and infant bone mineral content depletion), all other adverse birth outcomes and maternal and infant adverse events can be housed within this sample size and will have smaller D as the relative prevalence decreases toward 0 i.e. narrower equivalence zones. Assuming a loss to follow-up of 5%, we would need 442 women in each group (884 in both arms combined) for the two year time frame of the study.

Outcome	n/N	Prevalence	Required sample size in each group for proposed equivalence trial	Total required sample size for proposed equivalence trial
Pre-term	1096/5916	18.5%	421	842
LBW	651/5916	11.0%	274	548
Small for GA	429/5916	7.3%	189	378
VLBW	141/5916	2.4%	64	128
Stillbirth	130/5916	2.2%	58	116

Main endpoint 1: sample size for safety in pregnancy for birth outcomes Prevalence adverse birth outcomes among HIV-ve (in descending order)

Based on a non-inferiority trial design: A sample size of 421 in the treatment group and 421 in the control group (i.e. 842 in total) achieves 80% power to detect a non-inferiority margin difference between the group proportions of 0.075 or 7.5%. The reference group proportion (pre-term delivery birth outcome) is 0.185 or 18.5%. The treatment group proportion is assumed to be 0.26 or 26% under the null hypothesis of inferiority. The power was computed for the case when the actual treatment group proportion is 0.185 or 18.5%. The test statistic used is the two-sided Z test (unpooled). The significance level of the test was targeted at two-sided 0.05 or 5%.

Secondary Endpoint

PASS 12 sample size software (Hintze, J. (2013). PASS 12. NCSS, LLC. Kaysville, Utah, USA. www.ncss.com) was to calculate this sample size. In order to show a 50% reduction in HIV infections, with significance level of 0.05 or 5% and 80% power, we would need to observe 66 HIV infections in total (44 in control arm [cumulative incidence of 12.72%] and 22 in the intervention arm [cumulative incidence of 6.36%]). This assumes an HIV incidence of 3 per 100 person years during the 6 months of pregnancy and 6 per 100 person years during the 18 months of breastfeeding [9]. Based on these assumptions, we would require 334 subjects in group or 668 in total. Assuming a loss to follow-up of 10%, we would need to increase this to 346 women in each group (692 in both arms combined) for the two year time frame of the study.

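### Maternal bone density has no margin, SD or sample size of its own; the 4-7% printed for mothers is an infant detectable difference and, if used as a maternal margin, exceeds the TDF losses the protocol cites.

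*Combined protocol and SAP*

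**What the plan says.** Section 10.2 lists bone mineral density among women as part of the main outcome measure, alongside bone density and growth in infants.

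Section 10.3 covers both under one subheading, "Maternal and Infant Bone Mineral Density (4-7% margin difference". The paragraph below it does two separate things:

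- **Mothers.** It cites a substudy of women randomised to TDF-containing ART or infant nevirapine. For lumbar spine the arm comparison is "mean difference -3.16% (-4.44, -1.87"; for hip it is "mean difference of -2.33% (-3.23, -1.42". Both have p < 0.001. No maternal sample size, SD or limit follows.
- **Infants.** It gives a sample size, "We would require 150 infants exposed to maternal PrEP (TDF/FTC) and 150 infants unexposed (control group", chosen to "detect a pair-wise difference of 4-5% in mean WB-BMC and 6-7% in mean LS-BMC". No SD is stated here either.

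The section then refers to bone mineral content depletion in mothers and infants, says that "all other adverse birth outcomes and maternal and infant adverse events can be housed within this sample size", and promises narrower equivalence zones as prevalence falls. The only value defined as an acceptance limit is 7.5 percentage points, on event proportions.

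Section 10.4 plans Fisher's exact test and then two one-sided tests after describing adverse-event counts. It adds a hierarchical or random-effects non-inferiority analysis for the primary endpoints. It gives no bone margin or decision rule and leaves full detail to a later SAP.

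**The concern.** The subheading joins mothers and infants and calls 4-7% a margin, but both parts of the range, 4-5% and 6-7%, belong to infant whole-body and lumbar-spine content. Mothers have inherited a number that was not worked out for them.

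This matters because a non-inferiority analysis of maternal bone density needs a limit, and this is the only bone figure in the document labelled as one. Every value in it is larger than the two maternal losses quoted in the next paragraph. An analyst who took the label at face value could report maternal bone as non-inferior in a trial that had reproduced the loss cited for TDF. The trial is open label and the SAP is to be written after enrolment begins, so the limit is best settled now.

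**Working it through.** **Inputs from the documents**
- Maternal spine: difference 3.16%, 95% CI 1.87 to 4.44 (10.3, as losses).
- Maternal hip: difference 2.33%, 95% CI 1.42 to 3.23 (10.3, as losses).
- 442 women per arm (10.3); retention target 90% per year (7.17); two-year time frame (10.3).
- Two-sided 5% level (10.3, stated for preterm delivery).

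**Inputs assumed**
- The SD of maternal percent change is not stated. It is back-calculated below for an assumed 100 to 250 women per arm in the cited substudy.
- Women scanned per arm: 442 × 0.90 × 0.90 = 358.

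**The plan's own figures**
- The 421 per group for preterm delivery (18.5%, margin 7.5 points, 80% power, one-sided 0.025) reproduces exactly.
- The 150 infants per group cannot be reproduced, because no SD is given. Solving backwards, SD = difference / [(1.96 + 0.842) × √(2/150)], gives 12.4%, 15.5%, 18.5% and 21.6% of the mean for differences of 4, 5, 6 and 7%.
- The cited maternal differences agree with their arm-level figures: −2.06 − 1.09 = −3.15 and −5.37 + 3.05 = −2.32, equal to the stated values apart from rounding.

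**The range against the cited losses**
- Spine: 4/3.16 = 1.27 and 7/3.16 = 2.2 times the cited loss.
- Hip: 4/2.33 = 1.72 and 7/2.33 = 3.0 times.
- On confidence limits, which is how non-inferiority is judged, the cited hip result (worst limit 3.23) lies inside the whole 4-7% range. The cited spine result (worst limit 4.44) fails at 4% and passes at 5-7%.

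**Back-calculated SDs**
- SE = CI width / 3.92: spine (4.44 − 1.87)/3.92 = 0.656; hip (3.23 − 1.42)/3.92 = 0.462.
- SD = SE × √(n/2), n = 100 to 250: spine 4.6 to 7.3; hip 3.3 to 5.2.

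**Chance of declaring non-inferiority when the true loss equals the cited loss**

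P = Φ[(margin − loss)/SE − 1.96], with SE = SD × √(2/358).

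| Site (true loss) | SD | SE | Margin 4% | Margin 5% | Margin 7% |
|---|---|---|---|---|---|
| Hip (2.33%) | 3.3 | 0.247 | about 100% | about 100% | about 100% |
| Hip (2.33%) | 5.2 | 0.389 | 99% | about 100% | about 100% |
| Spine (3.16%) | 4.6 | 0.344 | 69% | about 100% | about 100% |
| Spine (3.16%) | 7.3 | 0.546 | 34% | 92% | about 100% |

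Example, spine with SD 7.3: at 4%, (4 − 3.16)/0.546 − 1.96 = −0.42, so 34%; at 5%, (5 − 3.16)/0.546 − 1.96 = 1.41, so 92%.

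**Power simply to detect the cited losses**

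Power = Φ(loss/SE − 1.96). At the larger SDs: hip 2.33/0.389 − 1.96 = 4.03; spine 3.16/0.546 − 1.96 = 3.83. Both exceed 99%.

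**The case against.** A reader might infer that the protocol has decided to accept the known TDF bone loss as safe. The documents do not support that.

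- No sentence says that a maternal loss below 4-7% will be tolerated. The body text presents the figures as infant differences to detect.
- The section uses the label loosely. The neighbouring 2% margin for maternal adverse events is just the observed 3% minus 1%.
- The two one-sided tests in 10.4 follow the comparison of adverse-event counts and are not tied to bone density. Only the later modelling sentence reaches the primary endpoints, and counting maternal bone among them rests on its being a main outcome in 10.2.
- Nor is the trial too small to see the cited losses. A loss of that size would almost certainly give an interval excluding zero.
- The benchmark is indirect. It compares TDF-ART with infant nevirapine in HIV-infected women. For HIV-uninfected Truvada users, section 1.10 reports changes of −0.4% to −1.0% relative to placebo.
- The scales differ: percent change over time in mothers, difference in mean content in infants.

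All of this stands, and it rules out the stronger reading. It does not supply what is missing. Section 10.3 places bone depletion within its equivalence zones, but the reason it gives, prevalence falling toward zero, cannot produce a limit for a continuous percent change. A planned non-inferiority analysis of maternal bone would therefore find only the mislabelled infant range.

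**Conclusion.** The point holds in a conditional form. The subheading assigns mothers an infant detectable difference, and maternal bone density, a main outcome, has no margin, SD or sample size of its own.

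If 4-7% were applied as the maternal margin, a true loss equal to the cited hip effect would be declared non-inferior about 99-100% of the time at 4% and about 100% at 5-7%. For the cited spine effect the chance is about 34-69% at 4%, above 90% at 5% and about 100% at 7%. The spine result at 4% is thus uncertain rather than a near-certain pass.

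These figures rest on 358 women scanned per arm, on SDs derived from an assumed 100 to 250 per arm in the cited substudy, and on judging by a 95% CI. They describe what the label permits, not a decision rule that the sponsor has adopted. Lack of power is not part of the point.

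**What to change.** In 10.3, restrict 4-7% to infant bone mineral content, call it a detectable difference, and state the infant SD.

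For maternal hip and spine density, choose one of two courses and write it into the protocol or SAP before any comparison by arm:

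1. Pre-specify separate, justified non-inferiority limits for hip and spine, each smaller than the cited effect (2.33% hip, 3.16% spine). Take account also of the −0.4% to −1.0% changes in section 1.10, since a limit just under the cited effects would still pass all of that. State the SD and the percent-change measure used.
2. Report the difference between arms with its 95% CI, and make no equivalence or non-inferiority claim for maternal bone.

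The second course costs only wording. The cost of the first depends on the limit. As an illustration only, take half the cited effects (spine 1.58%, hip 1.165%), a true difference of zero, 80% power and 358 per arm. The largest SD that can be supported is limit / [(1.96 + 0.842) × √(2/358)] = limit / 0.209, which is about 7.5 for spine and 5.6 for hip. The back-calculated SDs (up to 7.3 and 5.2) just fit, but any real loss would reduce that power. Either way, a maternal bone-safety claim becomes harder to make.
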